The primary aim of the study is to assess the current incidence of major peri-intubation adverse events during anaesthesia in patients undergoing elective or emergency surgery and in the setting of nonoperating room anaesthesia. The secondary aim is to assess the current practice of airway management during anaesthesia worldwide.

STUDY DESIGN

International, multicenter, prospective cohort study.

POPULATION

Inclusion criteria

We will include all adult (≥ 18 years old) patients undergoing advanced airway management for general anaesthesia in operating room or non-operating room anaesthesia (NORA) locations. We will include all the procedures both diagnostic and therapeutic, elective, or emergency that will require an advanced airways management (either tracheal intubation or SGA placement).

All potentially eligible patients will be identified by local investigators by screening the OR schedule and the procedures performed outside the OR.

Exclusion criteria

We will exclude the airway management during cardiopulmonary resuscitation. Critical patients undergoing advanced airway management in ED, wards or ICU, due to their underlying clinical condition will not be included in the study.

PRIMARY OUTCOME

At least one of the following major adverse events occurring within 30 minutes from induction or up to surgical incision:

Major adverse event:

- Severe hypoxia (SpO₂ < 80%)
- Cardiovascular collapse (at least one of the following):
 - Systolic arterial pressure < 65 mmHg
 - Systolic arterial pressure < 90 mmHg for > 15 minutes
 - Unplanned need of vasopressors and/or fluid load > 15 ml/kg to maintain the target blood pressure.
- Cardiac arrest

Blood pressure values should be confirmed in two consecutive measurements on non-invasive blood pressure monitoring or for 10 seconds on invasive monitoring system.

SECONDARY OUTCOMES

- Minor adverse events:
 - Moderate hypoxia (SpO₂ < 93%)
 - Airway injury
 - Clinically relevant bleeding
 - Oral aspiration of gastric contents
 - Dental injury
- Difficult facemask ventilation
- First pass success rate
- Early cardiovascular collapse
- Late cardiovascular collapse

OTHER OUTCOMES

- Unplanned need for ICU admission secondary to airway management related complications
- Emergency front of neck airway (eFONA)
- Cannot intubate cannot oxygenate scenario (CICO)
- In-hospital mortality
- Post-procedural severe hypertension
- Difficult procedure (more than 2 attempts)

DATA COLLECTION

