Data will be collected real-time by an investigator not involved in airway management using either the paper or the electronic version of the case report form on the Redcap.

The following variables will be collected:

- Informed consent and admission data
- Demographic and clinical characteristics
- Type of procedure (time, setting, type of surgery, elective or emergency

- Airway evaluation (anticipated difficult airway management)
- Monitoring applied during the procedure
- Ongoing respiratory and hemodynamical support before intubation
- Patient's parameters
- Preoxygenation method and use of apnoeic oxygenation (position during preoxygenation, rapid sequence induction applied)
- Fraction of expired O₂ (FeO₂) at the end of preoxygenation
- Application of any apnoeic oxygenation method
- Application of rapid sequence induction intubation
- Drugs used for induction (molecules and doses)
- Elective method for advanced airway management
- Operator's characteristics
- Method used for the second (and following) attempt
- Method used for adequate tube placement confirmation
- Duration of airway management procedure
- Outcome of endotracheal intubation (total number of attempts, laryngoscopic view, minimum SpO₂ during laryngoscopy, need for LMA)
- Advanced airway management-related complications (severe cardiovascular collapse, severe and mild hypoxemia, cardiac arrest, airway injury or any bleeding, aspiration of gastric contents, dental injury, emergency front of neck airway (FONA), cannot intubate cannot oxygenate scenario (CICO), unplanned need for ICU secondary to airway management complications)
- Extubation procedure
- In-hospital mortality

Local investigators are expected to transfer all collected data into an electronic CRF (eCRF, Research Electronic Data Capture – RedCap). Each local investigator will be trained on how to use the eCRF and will receive a personalized username and password. Each patient will be coded through a patient identification number generated by the eCRF and no patient names or initials will be present on the paper CRF.

Data will be handled confidentially and the paper CRF will be stored behind a lock at each local site. Any source of information which may allow to link a record with a patient will be destroyed at the end of the monitoring phase.

STATISTICAL ANALYSIS

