We will report mean and standard deviation of normally distributed variables and we will compare them using the student T-test. We will report non-normally distributed variables as median and interquartile range, comparing them using the Mann-Whitney U test. Categorical variables will be expressed as proportion and compared using the Chi-square or Fisher exact test as appropriate. We will perform a bivariate analysis to identify variables associated with the composite outcome of major peri-intubation adverse events and significant variables will be then used to construct a multivariate logistic model in order to identify independent variables.

The following planned secondary analyses will be performed:

- Place of intubation: OR vs NORA
- Type of surgery: cardiac vs non-cardiac surgery, ear-nose-throat surgery, thoracic surgery
- Urgency of the procedure: planned advanced airway management vs unplanned advanced airway management
- Type of hypnotic drug used: propofol vs different drug
- Airway management procedure: difficult airway management vs not difficult
- Patient's condition:
 - ASA 1-2 vs ASA 3-4;
 - BMI<30 vs BMI>30;

A two-sided p-value < 0.05 will be considered statistically significant. Statistical analysis will be performed by R 3.6.2 (http://www.R-project.org)

Sample size

Post-intubation hypotension has been reported in up to 10% of patients [11].

We aim to collect data on 1000 major peri-intubation events during anesthesia in order to include at least 10 putative variables associated with this event in planned analyses and sub-analyses, therefore we plan to recruit a total of 10.000 patients. Considering a 5% data lost, our final sample size will be of 10500 patients. We estimated an average number of 50 intubations/week at each centre so we plan to recruit a total number of 210 centres.

CENTRES RECRUITMENT

We will recruit academic and non-academic hospitals worldwide. Any centre that performs advanced airway management in the context of general anesthesia for either surgery or diagnostic/therapeutic procedures will be eligible for participation. Centers characteristics (academic vs non-academic, workload etc.) will be collected.

We will launch a website (www.stargate.com) and a social media channel (@stargate_study) where we will publish study information and documents (e.g. protocol, case report form, national coordinator list) which will be available for potentially interested investigators.

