APPENDIX 1 – TABLE WITH STUDY DEFINITIONS

Airway injury	Any detectable and clinically relevant injury attributable to tracheal intubation procedure (e.g bleeding, tracheal or bronchial tear or laceration)
Advanced airway management	The use of either a supraglottic airway device or tracheal intubation as airway management method to provide general anesthesia
Cannot Intubate Cannot Oxygenate Scenario (CICO)	Impossibility to achieve a successful tracheal intubation and adequate patient's oxygenation.
Cardiac arrest	Pulseless dysrhythmia occurring during/after advanced airway management
Cardiovascular collapse	 At least one of the following, occurring within 30 minutes from advanced airway management or up to surgical incision: SAP < 65 mmHg SAP < 90 mmHg for > 15 minutes or up to incision if it comes before 15 min Unplanned need of vasopressors and/or fluid load > 15 ml/kg to maintain the target blood pressure.
Early cardiovascular collapse	Any cardiovascular collapse event occurring up to 10 minutes from induction (or surgical incision, whichever come first)
Late cardiovascular collapse	Any cardiovascular collapse event occurring from 11 to 30 minutes from induction (or surgical incision, whichever come first)
Clinically relevant airways bleeding	Any sign or symptom of airways haemorrhage that meet at least one of the following criteria: • requiring medical intervention by a healthcare professional • leading to hospitalization or increased level of care • Prompting a face to face evaluation
Dental trauma	Fracture or avulsion of tooth during airway management

Difficult mask ventilation	Impossibility to provide adequate ventilation because of one or more of the following problems: inadequate mask seal, excessive gas leak, or excessive resistance to the ingress or egress of gas
Difficult tracheal intubation	Procedure requiring > 2 laryngoscopy attempts
Duration of the airway management procedure	Difference between time of confirmed airway device placement and preoxygenation start
Emergency front of neck access (eFONA)	Emergency need for invasive access to the patient's neck to provide adequate oxygenation (e.g. cricothyroidotomy, percutaneous tracheostomy, surgical tracheostomy).
Severe hypertension	Systolic arterial pressure > 180 mmHg
Attempt	Each time a device (SGA, laryngoscope, fiberscope) is introduced in patient's mouth/nose.
Moderate Hypoxia	SpO ₂ < 93%

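### Several stated subgroup and secondary-outcome categories fail as written: ASA 5 and BMI of exactly 30 have no group, airway injury omits supraglottic patients, and moderate hypoxia has no lower bound

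*Protocol*

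**What the plan says.** The Statistical Analysis section lists planned secondary analyses. Two are splits on patient condition: "ASA 1-2 vs ASA 3-4" and "BMI<30 vs BMI>30". The synopsis has the same two splits. A third reads "Urgency of the procedure: planned advanced airway management vs unplanned advanced airway management"; the synopsis words it in terms of intubation.

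The inclusion criteria begin "We will include all adult (≥ 18 years old) patients undergoing advanced airway management for general anaesthesia in operating room or non-operating room anaesthesia (NORA)". They add that elective and emergency procedures both qualify, and that advanced airway management means either tracheal intubation or a supraglottic airway (SGA). No ASA or BMI limit appears.

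Appendix 1 defines airway injury as "Any detectable and clinically relevant injury attributable to tracheal intubation procedure". The Data Collection section lists airway injury among the complications of advanced airway management.

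Under Secondary Outcomes, the first minor adverse event is given as "Moderate hypoxia (SpO₂ < 93" per cent, and Appendix 1 repeats that single threshold. Severe hypoxia, SpO₂ below 80%, is a component of the primary outcome.

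The Data Collection list has an item that begins "Type of procedure (time, setting, type of surgery, elective or emergency".

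**The concern.** A subgroup contrast should give every eligible patient exactly one place, and an outcome definition should be attainable by everyone in its denominator. The stated rules break this in three places.

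- **No group.** The ASA and BMI splits each leave out some eligible patients. For ASA, those left out are at the high-risk end of the factor being examined.
- **Outcome not attainable.** Read literally, a patient managed only with an SGA cannot have an airway injury but still counts among those at risk.
- **Overlapping grades.** The label 'moderate' suggests a grade below severe, but the threshold takes in every severe case, so one desaturation is both a major and a minor event.

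In addition, the urgency contrast is named for the procedure but split on a property of the airway management that the protocol does not define.

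This study exists to report incidences, and its dataset will later be shared for secondary analyses. Definitions that sites and later analysts can apply in different ways lead directly to different reported rates.

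**Working it through.** **The plan's own figure.** Target events ÷ assumed rate = 1000 ÷ 0.10 = 10,000; with 5% added, 10,000 × 1.05 = 10,500; and 210 centres × 50 patients = 10,500. The figure reproduces, and no category discussed here enters it. The primary composite uses SpO₂ below 80%, cardiovascular collapse and cardiac arrest, and none of these changes either.

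**1. ASA and BMI groups.** Eligible: all adults, elective or emergency, with no ASA or BMI limit. Excluded: airway management during resuscitation, and critical patients whose airway is managed because of their underlying condition. A patient of the highest ASA class brought to the operating room for emergency surgery is being anaesthetised for the operation, so neither exclusion removes that patient. Groups offered: ASA {1, 2} and {3, 4}, leaving out class 5 of the standard scale; BMI below 30 and above 30, leaving out 30.

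The protocol gives no BMI or ASA distribution, so the sizes are assumptions. Take BMI as normal with mean m and SD s. The share recorded as 30 is Φ((30 + w − m)/s) − Φ((30 − w − m)/s), with w = 0.05 for one decimal and w = 0.5 for whole numbers.

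| Assumed mean, SD | One decimal | Whole numbers |
|---|---|---|
| 24, 4 | 0.32% (32 of 10,000) | 3.2% (325) |
| 26, 5 | 0.58% (58) | 5.8% (579) |
| 28, 6 | 0.63% (63) | 6.3% (628) |
| 28, 4 | 0.88% (88) | 8.8% (878) |

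Over means 24–28 and SDs 4–6 this is about 0.3–0.9% to one decimal and 3–9% if rounded. For ASA 5, an assumed share of 0.1–1% gives 10 to 100 of 10,000.

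**2. Airway injury.** Let p be the share of patients managed with an SGA only, and let r_T and r_S be the injury risks with intubation and with an SGA.

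- True rate: (1 − p)·r_T + p·r_S
- Rate under the literal definition: (1 − p)·r_T
- Shortfall: p·r_S

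The shortfall is above zero whenever SGA patients are enrolled and can be injured. The documents give neither p nor the risks, so no size can be attached.

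**3. Moderate hypoxia.** Any SpO₂ below 80% is also below 93%. Hence rate(moderate, as written) = rate(80% ≤ lowest SpO₂ < 93%) + rate(lowest SpO₂ < 80%). The excess equals the severe-hypoxia rate exactly: an assumed 0.1–2% gives 10 to 200 of 10,000. Whatever that rate is, all severe cases are counted in both grades.

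**4. Urgency.** Side by side: the label refers to the procedure; the split refers to whether airway management was planned; the variable collected is elective or emergency. Appendix 1 defines neither planned nor unplanned. An emergency operation can have a fully planned intubation, and an elective procedure outside the operating room can come to need unplanned airway management. The split may therefore differ from procedural urgency, and none of the listed contrasts uses the collected variable by name.

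**The case against.** The strongest reply is that all this is secondary and small. ASA 5 patients leave one contrast only and remain in the primary incidence. Suggested screening covers three to five operating rooms plus non-operating-room cases, so they may be very few. Nested hypoxia thresholds mislead only if grades are added or read as exclusive, and no combined total is announced; Data Collection lists severe and mild hypoxemia as separate items. Airway bleeding and dental trauma are defined without reference to device, so some SGA injury is captured elsewhere. All of that stands and limits the weight of the point. It does not make the stated categories right.

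Some stronger readings are tempting but unsupported:

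- *Emergency cases all fall in the planned group.* The term is undefined and could be meant as scheduled versus unscheduled, that is, elective versus emergency. Only a possible mismatch is shown.
- *The surgery groups overlap and must be made exclusive.* The line "Type of surgery: cardiac vs non-cardiac surgery, ear-nose-throat surgery, thoracic surgery" can be read as separate contrasts, and overlap between separate contrasts is no error.
- *Patients below 93% before induction should be excluded from moderate hypoxia.* That is a design preference. It also rests on a pre-induction SpO₂ that Data Collection does not name.
- *Recorded injury is 60–80% of the true rate.* This needs an SGA share of 20–40% and equal risk by device, neither of which is in the documents.
- *About 660 patients have BMI exactly 30.* This needs BMI stored as whole numbers, which nothing in the protocol suggests.

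**Conclusion.** The point holds, limited to secondary analyses and secondary outcomes. Three stated rules are wrong as written: the ASA and BMI splits are not exhaustive, the airway-injury definition excludes a device that the cohort includes, and moderate hypoxia contains severe hypoxia. The urgency split is an undefined term that may not match its label.

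The BMI and ASA gaps are probably small: about 0.3–0.9% for BMI recorded to one decimal and 1% or less for ASA 5, both resting on assumed distributions. The hypoxia overlap is certain in logic, and its size equals whatever severe-hypoxia rate is observed. The airway-injury shortfall cannot be sized from the documents, but it matters most in practice: that definition governs what sites record, so an injury never entered cannot be fully recovered at analysis. A separate analysis plan could refine the groupings, but the protocol states these cut-points and definitions itself, so this is not a matter of detail left for later.

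**What to change.** - Compare ASA 1–2 with ASA 3 or above, and BMI below 30 with BMI 30 or above.
- Define airway injury as attributable to advanced airway management, and report it by device.
- Define moderate hypoxia as lowest SpO₂ of at least 80% and below 93%.
- Base the urgency contrast on the elective/emergency variable already collected.

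Make the ASA, BMI and urgency changes in the synopsis as well as the main text.

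The cost is a small amendment to the definitions, plus a site instruction on airway injury. Elective/emergency status is named in Data Collection. The sponsor should confirm that the case report form accepts airway injury in SGA patients and separates the two hypoxia grades, since the list names minimum SpO₂ only during laryngoscopy. If any centre has already enrolled under the narrower injury definition, report that period separately.

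### The secondary analyses by patient condition use BMI and ASA class only as two groups, which loses information on weak graded effects and can hide a U-shaped BMI relation

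*Protocol*

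**What the plan says.** The Statistical Analysis section introduces a list with "The following planned secondary analyses will be performed". Under patient's condition the list has two entries: "ASA 1-2 vs ASA 3-4" and "BMI<30 vs BMI>30". The synopsis repeats both. Neither place gives a reason for the cut points or says what is to be estimated within or between the groups.

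Finding risk factors is described separately, just before that list: "We will perform a bivariate analysis to identify variables associated with the composite outcome of major peri-intubation adverse events". The significant variables then go into a multivariable logistic model. The coding of BMI and ASA in that model is not stated. For comparing continuous variables the section provides a t-test or, where they are not normal, a rank test: "We will report non-normally distributed variables as median and interquartile range, comparing them using the Mann-Whitney U test". The significance rule is "A two-sided p-value < 0.05 will be considered statistically significant".

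The Sample size section aims at 1,000 events "in order to include at least 10 putative variables associated with this event in planned analyses and sub-analyses". It states no effect size, BMI distribution, ASA distribution or power for any contrast.

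**The concern.** BMI is continuous and ASA class is ordered. A single cut treats a patient with BMI 18 like one with BMI 29, and ASA 1 like ASA 2. If risk changes gradually across the scale, the two-group contrast uses only part of the information collected. Two things are at stake in these secondary analyses:

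- A weak graded association may be missed that the same patients could have shown.
- If risk is raised at both low and high BMI, one cut at 30 mixes low-risk and high-risk patients below it. The contrast may then be reported as no association. A larger sample does not correct that distortion of shape.

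The binary primary outcome is not in question, because an incidence needs a defined event. The primary incidence estimate is not affected.

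**Working it through.** **Inputs from the protocol.** 1,000 target events, a 10% event rate, 10,000 patients, 5% data loss, two-sided alpha 0.05. The plan's own size reproduces: 1,000 / 0.10 = 10,000, and 10,000 x 1.05 = 10,500.

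**Assumptions, because the protocol gives no figures.** BMI is normal on a suitable scale with 15%, 25% or 35% of patients above 30. ASA classes 1-4 follow one of three mixes. The effect is linear on the log-odds scale unless stated otherwise.

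**Information kept by the BMI cut.** With s the share above 30, c the matching normal quantile and phi the normal density, the share kept is phi(c)^2 / [s(1-s)].

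- s = 0.15: 0.426, a loss of 57%
- s = 0.25: 0.539, a loss of 46%
- s = 0.35: 0.603, a loss of 40%

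**Information kept by the ASA cut.** This is the squared correlation between the 1-4 score and the two-group indicator. For the mix 25/45/27/3%, the score variance is 4.96 - 2.08^2 = 0.6336, the indicator variance is 0.30 x 0.70 = 0.21 and the covariance is 0.93 - 2.08 x 0.30 = 0.306. So 0.306^2 / (0.6336 x 0.21) = 0.704. The mixes 15/45/35/5% and 35/45/18/2% give 0.744 and 0.638. The loss is therefore 26-36%.

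**Power.** Expected z = ln(OR per SD) x sqrt[N q (1-q)], with q the event rate, multiplied by the square root of the share kept when the variable is cut. With N = 10,000 and q = 0.10 the root is sqrt(900) = 30. At OR 1.10, z = 0.0953 x 30 = 2.86 uncut and 2.86 x sqrt(0.426) = 1.87 with the cut at s = 0.15.

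| Events | OR per SD of BMI | Linear term | Cut, 15% / 25% / 35% above 30 |
|---|---|---|---|
| 1,000 | 1.10 | 82% | 46% / 56% / 60% |
| 1,000 | 1.15 | 99% | 78% / 87% / 90% |
| 1,000 | 1.20 | >99% | 95% / 98% / 99% |
| 500 | 1.20 | 98% | 74% / 83% / 87% |

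For ASA with 1,000 events and OR 1.15 per class, power is 90-92% with the ordered score and 73-81% with the cut. At OR 1.30 per class the cut has about 99.8% even under the least favourable of the three mixes.

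**Simulation check of the linear case** (2,000 runs per setting, OR 1.10). Uncut power was 82-84%. With the cut it was 49% with 15% above 30 and 62% with 30% above.

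**Cost of a flexible term.** The linear-term figures overstate what a spline gains. In simulation (400 runs, 25% above 30), a spline tested on 3 degrees of freedom had 68% power at OR 1.10, between 83% for a linear term and 57% for the cut. At OR 1.15 the figures were 95.5%, 99.5% and 87%.

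**Other shapes.**

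- *U-shape* (log-odds rising 0.08 per squared SD, 300 runs): with 15% / 25% / 35% above 30, power was 44% / 22% / 10% with the cut and 83% / 88% / 84% with a 4-knot spline.
- *True step at 30* (30% above, step OR 1.25): the cut has 87% power and a linear term 64%. In simulation the cut had about 90% and the spline 58%.

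**The case against.** The strongest reply is that these entries are not the protocol's risk-factor analysis. That task belongs to the bivariate screen and the logistic model, and nothing there says that BMI is cut or ASA classes are merged. The t-test and rank-test provisions allow BMI to be compared uncut. The patient-condition entries stand beside contrasts such as OR against NORA and propofol against another drug, so they can be read as subgroup reporting. Event rates by group need groups, and the obesity split is familiar to readers.

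Most of this stands. A reader might infer that the study as a whole loses power to relate BMI and ASA to the primary composite, or that coarse adjustment leaves residual confounding in the multivariable model. The protocol supports neither inference. It does not say that the two-group forms enter that model, and such coding is commonly left to a statistical analysis plan, which was not available here.

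It is also fair that the size of the loss rests on assumed distributions and a linear effect, that 1,000 events largely absorb the loss at an odds ratio of 1.20 per SD or more, and that a true step at 30 reverses the advantage.

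The reply does not remove the named contrasts. They are the only form in which these patient-condition analyses are specified, no reason is given for preferring a step at 30, and the uncut location tests in the screen can themselves miss a U-shape.

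**Conclusion.** The point holds as a modest, cheaply corrected inefficiency in two named secondary analyses. Under a graded effect the BMI cut loses about 40-57% of the information (15-35% of patients above 30) and the ASA cut about 26-36% (three assumed class mixes). These are separate ranges for separate variables. A reader might merge them into one 26-57% loss set by the plan, but none of these percentages comes from the protocol.

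At the planned 1,000 events the loss in power is material for weak effects, at odds ratios of about 1.10-1.15 per SD, and small at 1.20 or above. It grows if events fall well short: with 500 events and an odds ratio of 1.20, a linear term has 98% power and the cut 74-87%. That case is worth covering because the planned 10% is an upper figure reported for hypotension, not an estimate for the composite.

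The risk of hiding a U-shaped BMI relation is real but depends on a curvature that the protocol does not suggest. Confounding in the multivariable model would arise only if the two-group forms were used there.

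**What to change.** In the patient-condition secondary analyses, add as the main association analysis a logistic model of the primary composite on continuous BMI with a flexible term, such as a restricted cubic spline with 4 knots, and on ASA class as recorded (ordered score or separate classes). State that the same forms are used if BMI and ASA enter the multivariable model. Keep the two-group event rates as descriptive rows, and make the same change in the synopsis.

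The cost is a sentence or two in the statistical section and a little more analysis, with no new patients or data items. The downsides are small: a few extra degrees of freedom (3 instead of 1 for BMI), which about 1,000 events can carry; a curve instead of one contrast; and lower power than the cut if risk truly steps at 30.

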The project will be presented and a call for centres will be announced during international meetings of anesthesiology.

We will also apply for receiving the endorsement of international scientific societies in order to promote and enhance participation to this study.

PATIENTS RECRUITMENT

After obtaining the local approval, each center will select a start date and screening for patients' eligibility will start. In order to avoid selection bias while addressing study feasibility and balance across different participating centers, a maximum number of 50 patients from each center will be enrolled. To maintain data collection feasible, optimize enrolment of all consecutive patients, especially for high-volume centers, and balance number of enrolled patients across different centers, we suggest to focus screening for enrolment from a pre-defined number of operating rooms (3 to 5 according to local workload) up to the final enrollment of 40 patients/center in the anesthesia setting without any time limitation. All consecutive patients undergoing advanced airway management in the NORA setting will be screened up to the final enrollment of 10 patients/center without any time limitation. Local investigators will be involved in the screening of operating list of those selected areas.

Screening of all consecutive patients will involve all patients treated in the selected areas of each center. Screening and reporting of all consecutive treated patients will be interrupted only when the target number of patients/center will be reached.

PUBLICATION AND AUTHORSHIP POLICY

The main results of STARGATE study will be published in a peer—reviewed international medical journal. Authorship policy will follow the International Committee of Medical Journal Editors (ICMJE) recommendations. Authorship will be considered based on contributions to recruitment of patients, data acquisition and cleaning, analysis and interpretation of the data, manuscript writing, submission of national/local grants AND final approval of the version to be published AND agreement to be accountable for all aspects of the work, in ensuring that questions related to the accuracy or integrity of any part of the work are appropriately investigated and resolved.

Dipartimento Oncologia

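### The target of 1,000 events treats two upper limits as expected values: a rate of up to 10% for a different outcome, and a maximum of 50 patients per centre

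*Protocol*

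**What the plan says.** The Sample size text under Statistical Analysis starts from one literature figure: "Post-intubation hypotension has been reported in up to 10% of patients". It then sets the target and its reason: "We aim to collect data on 1000 major peri-intubation events during anesthesia in order to include at least 10 putative variables". The sentence goes on to say that these variables serve the subgroup work as well as the main analyses, and derives 10,000 patients from the target. It allows for loss: "Considering a 5% data lost, our final sample size will be of 10500 patients". It then turns patients into centres: "We estimated an average number of 50 intubations/week at each centre so we plan to recruit a total number of 210 centres". The synopsis repeats these figures without the ten-variable reason.

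Three other places bear on the inputs:

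- **Primary outcome.** The endpoint is a composite: severe hypoxia, cardiovascular collapse or cardiac arrest. Collapse can be met by either of two systolic pressure criteria or by an unplanned need for vasopressors and/or a fluid load. No expected rate is given for this composite.
- **Patients recruitment.** The section fixes a cap: "a maximum number of 50 patients from each center will be enrolled". It describes the 50 as 40 in the operating-room setting plus a non-operating-room (NORA) part that "will be screened up to the final enrollment of 10 patients/center without any time limitation".
- **Reference 11.** By its title, the source of the 10% is a retrospective study of post-intubation hypotension in elective surgery patients.

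**The concern.** The event target depends on two quantities, the proportion of patients with the composite and the number enrolled per centre. The protocol enters the top of a range for both and treats it as the expected value.

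The rate also belongs to another outcome and population. Hypotension after intubation is one sign. The composite adds hypoxia, arrest and rescue treatment, and applies its own pressure limits. The cohort covers emergency procedures, NORA and supraglottic devices, whereas the cited study, by its title, concerns intubation in elective surgery.

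The per-centre figure is presented as weekly volume, but recruitment has no time limit and no number of weeks enters the calculation. What produces 210 is the cap of 50.

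At stake is what the 1,000 means. It reads as a number the design is built to deliver, and the multivariable and subgroup analyses are justified by it. The primary aim is an incidence, yet the stated basis for the size says nothing about how precisely that incidence will be known.

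**Working it through.** **Inputs from the protocol:** rate 10% (an upper figure, for hypotension); 1,000 events; at least 10 variables; 5% data loss; 210 centres; at most 50 patients per centre, of whom 10 are NORA.

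**1. The plan's own chain.**
- 1,000 / 0.10 = 10,000 patients
- 10,000 × 1.05 = 10,500
- 10,500 / 50 = 210 centres

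This reproduces exactly.

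**2. What 210 centres can deliver.**
- 210 × 50 = 10,500, the most they can enrol
- 10,500 × 0.95 = 9,975 analysable
- 9,975 × 0.10 = 997.5 events

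For each patient by which the average falls below 50, analysable patients drop by 210 × 0.95 = 199.5 and events at 10% by about 20, unless centres are added.

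**3. The loss allowance.** Covering 5% loss needs 10,000 / 0.95 = 10,526 patients, about 26 more than stated. The effect is 25 analysable patients and 2.5 events.

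**4. Sensitivity to the composite rate.** With n = 9,975, expected events are n × p. The 95% half-width is 1.96 × √(p(1 − p)/n) × √(1 + (m − 1) × ICC), where m = 9,975 / 210 = 47.5. The design effect is 1 + 46.5 × 0.05 = 3.325 at ICC 0.05 and 1 + 46.5 × 0.10 = 5.65 at ICC 0.10. The 5% and 20% rates and the non-zero ICCs are assumptions; the protocol gives none of them.

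| Composite rate | Expected events | Half-width, ICC 0 | ICC 0.05 | ICC 0.10 |
|---|---|---|---|---|
| 5% | 499 | 0.43 points | 0.78 | 1.02 |
| 10% | 998 | 0.59 points | 1.07 | 1.40 |
| 20% | 1,995 | 0.78 points | 1.43 | 1.87 |

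**5. The ten-variable reason.**
- 1,000 / 10 = 100 events per variable
- At an assumed 10 to 20 events per variable, ten variables need 100 to 200 events
- NORA subgroup at 10%: 210 × 10 × 0.95 × 0.10 = 199.5 events, about 20 per variable for ten variables

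A subgroup requirement could therefore explain a total near 1,000, but the protocol does not state that step or any events-per-variable rule.

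**The case against.** The strongest reply is that nothing is miscalculated. The chain is coherent, and at the stated inputs the design yields 997.5 of 1,000 events. That stands, so the point concerns the basis of the inputs. The 5% allowance is formally the wrong operation, but its effect is trivial.

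Four stronger readings are tempting, and the document does not support them.

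- **The study will fall short of events.** The direction of error is unknown. Severe hypoxia, arrest and any rescue vasopressor could push the composite above 10%. The pressure criteria (systolic below 65 mmHg, or below 90 mmHg for more than 15 minutes) could push it below. The cited study's definition is not given.
- **A centre's shortfall cannot be made up.** Other centres cannot exceed their cap, but any eligible centre may join, no upper limit on centres is stated, and enrolment has no time limit. Low volume alone need not leave a centre short.
- **1,000 events is wrong because ten variables need far fewer.** The sentence says at least ten, and extends to sub-analyses. An unstated step on the side of surplus is not a deficiency of events.
- **The lack of a precision statement is itself an error.** It is an omission that a statistical analysis plan might fill. It matters here only because precision is the sounder basis on which to restate the size.

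It is also fair that a lower rate would do limited harm. At 5%, 499 events would still support ten variables in the main model, and the incidence would still be estimated closely.

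**Conclusion.** The point holds narrowly. The protocol presents 1,000 events as the basis of its size, but it obtains them from an upper figure for a different outcome and from full enrolment at every centre. On its own inputs, 210 centres give no more than 9,975 analysable patients and about 998 events at 10%, with no margin. They give fewer if any centre stops short of 50 and none is added. Over assumed composite rates of 5% to 20%, the expected count runs from about 499 to 1,995, so a single fixed number is not supported in either direction.

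This does not show that the study is too small. Even with an assumed ICC of 0.10, the half-width at a 10% incidence is about 1.4 points. The planned size can stay; its stated justification should change.

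**What to change.** Keep 210 centres and reword the Sample size text, in the synopsis and the main body alike:

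1. State the size as 210 centres with at most 50 patients each, giving at most 10,500 enrolled and about 9,975 analysable after 5% loss. Drop the weekly volume as the source of 210, and say that centres may be added if enrolment per centre falls below the cap.
2. Replace the fixed 1,000 with expected events over composite rates on both sides of 10%, for example 499 at 5%, 998 at 10% and 1,995 at 20%. Say that the cited 10% is an upper figure for hypotension.
3. Tie the size to the primary aim: a 95% half-width at 10% incidence of about 0.6 points without clustering, 1.1 at ICC 0.05 and 1.4 at ICC 0.10, with the ICCs labelled as assumptions.
4. State the events-per-variable or smallest-subgroup rule behind the regression, or remove the claim that ten variables lead to 1,000 events.
5. Correct the loss allowance in passing: either 10,526 patients are needed, or 9,975 will remain.

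The cost is rewording, with no extra patients. The downside is that the stated figures become slightly less favourable.
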